### **3.3.2 Handling of Withdrawals**

When a subject withdraws from the study, the reason(s) for withdrawal will be recorded by the investigator on the relevant page of the electronic case report form (eCRF). Whenever possible, any subject who withdraws from the study if willing, should continue to be followed according to the protocol. For example, if termination occurs earlier than planned (i.e., after a subject has received all or partial study drug infusion) all efforts should be made to ensure the remaining protocol visits are completed. If a subject refuses to return for the Follow-up visits, the Day 28 ( $\pm 2$  days) visit procedures should be completed. Any subject who fails to return for final assessments will be contacted by the site in an attempt to obtain compliance with the protocol. The status of subjects who fail to complete final assessments will be documented in the eCRF.

### **3.3.3 Replacement of Subjects**

At the discretion of the investigator after consultation with the Sponsor, any subject who withdraws before completing the study, for reasons other than a DLT, may be replaced. Any replacement subject will be assigned to receive the same treatment as the subject he or she is replacing.

## **3.4 STUDY TREATMENTS**

### **3.4.1 Method of Assigning Subjects to Treatment Groups**

On Study Day 1 eligible subjects will be randomly assigned to treatment with either PB2452 or matching placebo in a 3:1 ratio, PB2452:placebo.

### **3.4.2 Treatments Administered**

#### **PB2452:**

PB2452 IV infusion, prepared according to the Pharmacy Manual, will be administered on Day 1 for up to 48 hours. The total dose for each subject will not exceed 30g. The infusion rate will not exceed 18g over 30 minutes and the concentration will not exceed 24g in 250mL. Subjects will not receive more than 250 mL of study drug infusion within any 1-hour period.

For each cohort, the dose, infusion rate, and duration will be communicated from the Sponsor to the study site, PPD, in a Dosing Memo issued prior to initiation of each treatment cohort.

#### **Matching Placebo:**

0.9% sodium chloride single IV infusion, administered on Day 1, will be delivered at a rate and volume matching the active infusion.

#### **Ticagrelor:**

Ticagrelor 90 mg oral tablet (immediate release) administered as 180 mg (2 × 90 mg tablets) loading dose plus 90 mg every 12 hours for 4 additional doses. In successive cohorts following cohort 1, if indicated in a Dosing Memo from Sponsor to site, one or more cohorts may also receive an additional single oral dose of 90

#### **ASA:**

During Screening, starting on Study Day -7, subjects will receive ASA (enteric coated) 81 mg QD to be taken through to the morning of Day 1, prior to receiving study medication.

Subjects who were already taking ASA daily before entering the study must be willing to document self-administered daily 81 mg dose of ASA between Day -7 and -3, accept ASA 81 mg administered at the clinical site between Day -2 and Day 1, and suspend further ASA doses until discharge from the clinical facility.

### **3.4.2.1 Dose Escalation**

The SRC will conduct a blinded review of all safety and tolerability data from a cohort at least through Day 3 (e.g., clinical laboratory results, AEs, ECGs, Holter monitoring reports if available, vital signs, and available PK data) and available data for each completed dose cohort and will document their review and assessment in written SRC minutes prior to initiation of a subsequent cohort. Dose escalation may occur only if the SRC affirms the dose and regimen from the previously completed cohorts were safe and well tolerated and no DLTs were observed.

The SRC will be minimally composed of the on-site PPD investigator/medical monitor, PhaseBio medical monitor, and PhaseBio clinical operations lead. Changes to the administration regimen (rate and duration) without escalation of the total dose or without

increases in the infusion rate will not require formal SRC approval. Similarly, reductions in the total dose or the infusion rate will not require SRC approval.

The investigator may make a recommendation concerning whether the safety profile is sufficient to proceed to a higher dose level, whether a pause in dosing for review of additional safety and/or PK data is needed, or whether adjustment of the dose of the next dose cohort is needed. The decision to adjust or pause the dose or proceed to the next cohort will be made by the SRC.

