### **Dose Escalation**

An SRC will be formed to conduct a blinded review of all safety and tolerability data (e.g., clinical laboratory test results, adverse events [AEs], ECGs, Holter monitoring report, vital signs) after each cohort- prior to initiation of a subsequent cohort. Escalation to a higher total dose of PB2452 will occur only if the SRC affirms the safety, tolerability, and absence of dose limiting toxicity (DLTs) in the preceding cohort(s).

The SRC will be minimally composed of the on-site PPD investigator/medical monitor, PhaseBio medical monitor, and PhaseBio clinical operations lead. Changes to the administration regimen (rate and duration) without escalation of the total dose or without increasing the infusion rate will not require formal SRC approval. Similarly, reductions in the total dose or the infusion rate will not require SRC approval.

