## 1.3 RATIONALE FOR DOSE SELECTION

In the first in human Phase 1 study of PB2452, 18 g administered as an initial 6 g bolus followed by a prolonged infusion of the remaining 12 g over 16 hours in healthy subjects aged 18-50 years old was considered generally safe and well tolerated. There were no PB2452-related adverse effects, injection site reaction (ISRs), or DLTs observed as determined by the study investigator and SRC. The profile of rapid and sustained ticagrelor reversal delivered by the 18 g dose level is potentially clinically meaningful and considered ideal for patients on ticagrelor with acute major bleeding or who need urgent surgery.

The 18 g dose level and prolonged infusion regimen administered in the Phase 1 study will be repeated in the current study in older and elderly subjects who are more similar in age and background comorbidities to the actual patient population treated with ticagrelor. Potentially longer infusions of PB2452 may be investigated in this study, using potentially higher total doses of PB2452. To mitigate any risks related to dose escalation, a Safety Review Committee (SRC) will be assembled to review all emergent safety and tolerability data and available PK data after each cohort is completed to determine whether dose escalation and/or prolongation of infusion duration is warranted. PK/PD modeling will be used to simulate potential doses, infusion regimens, and  $C_{max}$  and AUC exposure profiles prior to dose-escalation or adjustment of infusion regimen to ensure that no dose or infusion regimen

investigated in this study will exceed  $C_{max}$  or AUC exposures achieved at the no observed adverse effect level (NOAEL) in GLP toxicity study in rats.

In the rat GLP toxicity study, there were no adverse effects observed following single doses of PB2452 at the highest dose level tested of 2000 mg/kg given IV, alone or in combination with oral ticagrelor (20 mg/kg). Therefore, 2000 mg/kg was considered NOAEL with a maximum plasma concentration ( $C_{max}$ ) of 18100  $\mu$ g/mL and an area under the plasma concentration versus time curve from time zero extrapolated to infinity ( $AUC_{0-\infty}$ ) of 23100  $\mu$ g\*h/mL.

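### The exemption from formal SRC approval joins its two conditions with 'or', and it also waives approval of longer infusions that Section 1.3 places under SRC review

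*Protocol*

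**What the plan says.** The exemption is in Section 3.4.2.1 of the Part A protocol: "Changes to the administration regimen (rate and duration) without escalation of the total dose or without" increases in the infusion rate fall outside formal SRC approval. The Part A synopsis, under Dose Escalation, has the same rule: "without escalation of the total dose or without increasing the infusion rate will not require formal SRC approval". Section 3.4.2.1 and the synopsis of Part B repeat it, which makes four places in all. In each, the next sentence adds a second exemption: "Similarly, reductions in the total dose or the infusion rate will not require SRC approval".

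Two rules beside it point the other way on dose. Section 3.4.2.1 states: "Dose escalation may occur only if the SRC affirms the dose and regimen from the previously completed cohorts were safe and well tolerated". The Part A synopsis states: "Escalation to a higher total dose of PB2452 will occur only if the SRC affirms the safety, tolerability, and absence of dose limiting toxicity".

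Section 3.4.2.1 also keeps general SRC steps in place. The SRC "will document their review and assessment in written SRC minutes prior to initiation of a subsequent cohort", and "The decision to adjust or pause the dose or proceed to the next cohort will be made by the SRC".

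On duration, Section 1.3 of both parts says that the SRC reviews safety, tolerability and available PK data after each cohort "to determine whether dose escalation and/or prolongation of infusion duration is warranted".

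**The concern.** The exemption decides which changes of regimen need the committee's formal agreement, so its wording should not depend on the reader correcting it. Two separate problems appear.

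- **The conjunction.** With 'or', meeting either condition is enough. A change that raises the rate but not the dose is then exempt, and so is one that raises the dose but not the rate.
- **Prolongation.** The rule covers changes of rate and duration, and the next sentence exempts rate reductions. Stretching the same dose over a longer time is therefore exempt however the conjunction is read, although Section 1.3 lists prolongation among the matters that SRC review is to determine.

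Under Section 3.1 the Sponsor chooses later regimens and issues them by Dosing Memo. Where the exemption applies, the text leaves unclear whether the SRC must agree to the new regimen itself or only review the data from the previous cohort. Long infusions are foreseen: Section 1.3 says they may be investigated. The default schedule in Appendix 7.1 stops Holter recording 24 hours after the start of study drug, and its vital signs go from 60 minutes to 24 and then 48 hours. A 48-hour infusion would outlast the Holter recording, which is a matter for a safety committee to judge explicitly.

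**Working it through.** The plan gives no figure to reproduce. The check is one of logic, followed by simple rate arithmetic.

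**Inputs**
- Cohort 1 (Part A Section 3.1): 18 g in total, as 6 g over 10 min and then 12 g over 15 h 50 min (15.833 h), 16 h in all.
- Part A caps (Section 3.1): 30 g total dose, 48 h duration, 18 g over 30 min.

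**Step 1. What the sentence exempts**

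| Total dose | Infusion rate | Exempt with 'or' | Exempt with 'and' |
|---|---|---|---|
| not raised | not raised | yes | yes |
| not raised | raised | yes | no |
| raised | not raised | yes | no |
| raised | raised | no | no |

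The literal text exempts three of four combinations; 'and' leaves one.

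**Step 2. Faster infusion, same dose (row 2)**
- Cohort 1 maintenance rate: 12 / 15.833 = 0.758 g/h.
- Same 6 g bolus, 12 g over 7 h 50 min (7.833 h): 12 / 7.833 = 1.53 g/h.
- Ratio: 1.53 / 0.758 = 2.02.

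The protocol does not define whether rate means the rate of a phase or the average. The average also doubles: 18 / 8 = 2.25 g/h against 18 / 16 = 1.125 g/h. No other rule explicitly sends this change for SRC approval.

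**Step 3. Higher dose, same rates (row 3)**
- Running Cohort 1's rates on to 30 g: 24 / 0.758 = 31.67 h, plus 10 min of bolus, gives 31.83 h. Dose ratio: 30 / 18 = 1.67.
- This lies within the 30 g and 48 h caps and inside the literal exemption. It is also a dose escalation, which the neighbouring rule explicitly reserves for SRC affirmation. The two sentences contradict each other, and the explicit rule governs.

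**Step 4. Longer infusion, same dose (row 1)**
- Same bolus, 12 g stretched to the 48 h cap: 12 / 47.833 = 0.251 g/h, about one third of 0.758 g/h.
- Duration: 48 / 16 = 3 times Cohort 1.
- Neither dose nor rate rises, so the change is exempt with 'or' and with 'and'. It is exempt again as a rate reduction. Correcting the conjunction leaves the difference from Section 1.3 in place.

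These regimens are illustrations. No document proposes them.

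**The case against.** The case against giving this much weight is good, and most of it stands.

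- In ordinary usage, 'without X or without Y' often means neither, so this is an ambiguity and not evidence of intent.
- A reader might infer that a higher total dose can bypass the SRC. The documents do not support that: the escalation rule is explicit in the same section and in the synopses.
- A reader might infer that giving all 18 g in 30 minutes shows how much faster an infusion the 'or' releases. It does not show this cleanly. That regimen runs at 18 / 0.5 = 36 g/h, and Cohort 1's bolus already runs at 6 g per 10 min, also 36 g/h. No phase becomes faster. What changes is the amount given at the bolus rate, which a rate condition alone would miss.
- A reader might infer that Section 1.3 names SRC review as the safeguard against prolongation. Its stated purpose is to mitigate the risks of dose escalation; prolongation appears among the questions that the review is to settle.
- Sections 1.3 and 3.4.2.1 can be read together: the SRC reviews the data and decides whether to proceed, without separate formal approval of a slower infusion. Exempting a slower infusion is also defensible. Phase 1 exposure appeared dose-proportional (Section 1.1.2), so the same dose given more slowly should give a similar AUC and lower maintenance concentrations. Section 1.3 requires simulation against the rat NOAEL before any adjustment of the infusion regimen.

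Two things survive. The faster-infusion branch has no explicit counter-rule. And reviewing a past cohort's data is not the same act as agreeing to a new regimen; the text does not say which is required for a longer infusion.

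**Conclusion.** The point holds as a minor drafting defect in an operative safety rule. In all four places 'or' should be 'and': the literal text exempts a faster infusion of the same dose, about 2-fold in the maintenance phase in the example. It also contradicts the adjacent rule on total dose, but opens no real route to an unreviewed higher dose. Separately, and whatever the conjunction, same-dose prolongation up to three times Cohort 1's duration needs no formal approval, while Section 1.3 says SRC review is to determine whether prolongation is warranted.

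The practical effect is limited, because SRC data review, written minutes, the SRC's decision to proceed and the simulation step all remain. A reader might also infer that the exemption was misused. The documents give no ground for that: the SAP (Sections 3.1 and 3.3) reports a second Part A cohort at the same 18 g and no cohort after Cohort 3, and the Dosing Memos are not among the documents.

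The conclusion rests on the wording alone. The sizes assume Cohort 1 as the reference regimen and the Part A caps.

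**What to change.** In Section 3.4.2.1 and the synopsis of both parts, replace the two sentences with:

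> *Changes to the administration regimen that do not increase the total dose, and do not increase the infusion rate of any phase or the amount given at the bolus rate, and do not prolong the infusion beyond a duration the SRC has already reviewed, will not require formal SRC approval. Reductions in the total dose or the infusion rate will not require SRC approval, provided they do not prolong the infusion beyond a duration the SRC has already reviewed.*

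The clause on the bolus amount is needed because Cohort 1's bolus already runs at the Part A rate ceiling, so a larger bolus at that rate would otherwise pass. The second sentence waives only the reduction itself; a reduction paired with an increase elsewhere should be tested against the first sentence. Section 1.3 then needs no change.

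The cost is two sentences in four places. A few more regimen changes would need formal approval (a longer infusion, a faster phase or a larger bolus at the same total dose), and this can be given at the SRC reviews already scheduled before each cohort.

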### **3.4.2.2 Infusion-related or Allergic Reactions**

The administration of study drug infusion must be performed under supervision of trained medical staff and where facilities to handle allergic reactions are available. Should a subject experience symptoms typical of IRRs seen with some recombinant protein drugs e.g., lightheadedness, nausea, chills, fever([Doessegger 2015](#)) the study drug infusion must be immediately and permanently discontinued. Should a subject experience symptoms typical of an allergic reaction (e.g., shortness of breath, anaphylaxis, urticaria, angioedema), the study drug administration must be immediately and permanently discontinued. Suspected IRRs will be assessed according to the Common Terminology Criteria for Adverse Events (CTCAE) version 5.[\(NCI CTCAE, v5, 2017\)](#) Should any one subject develop a  $\geq$ Grade 2 IRR to study drug, all subsequent subjects in the study, inclusive of all dose cohorts, must be administered premedication (diphenhydramine 25 mg by mouth [PO] + acetaminophen 650 mg PO) 30 to 60 minutes prior to receiving study drug to mitigate the risk of IRR. If any recipient of PB2452 (after unblinding) develops a  $\geq$ Grade 2 IRR in the absence of premedication, the entire dose level must be repeated as an additional cohort in which all subjects must be premedicated (as described above) 30 to 60 minutes prior to administration of study drug.

To monitor for potential IRRs, vital signs, including BP, HR, Temp, RR, will be assessed at Baseline (prior to study drug infusion), every 10 minutes during the first 30 minutes of the infusion, and every 15 minutes thereafter for the first hour after initiation of the infusion. The remaining assessments of vital signs will be performed as described in the Schedule of Events ([Appendix 7.1](#)). Suspected allergic (hypersensitivity) reactions and anaphylaxis will be assessed according to the clinical diagnostic criteria outlined by the National Institute of Allergy and Infectious Diseases provided in the CTCAE v5 in [Appendix 7.3](#) (Definition and Management of Anaphylaxis) and [Appendix 7.4](#) (Clinical Criteria for Diagnosing Anaphylaxis). Subjects will receive appropriate medical treatment for these and other medical concerns at the discretion of the investigator.

### **3.4.2.3 Dose-limiting Toxicities**

The SRC will review all AEs and all laboratory and ECG Holter monitoring abnormalities according to CTCAE v5 to determine whether DLT has been identified in a subject who is confirmed to have received PB2452. If the SRC determines an AE is related to administration of ticagrelor or another confirmed cause, the AE will not be considered a DLT. Definitions of DLT are:

- Any AE assessed as  $\geq$ Grade 2 based on the CTCAE v5 grading scale and occurred in a subject confirmed to have received PB2452.
- Any  $\geq$ Grade 2 laboratory abnormality (outside the clinical laboratory normal reference range) that occurs in a subject confirmed to have received PB2452.
- Note: For a Grade 2 electrolyte abnormality that spontaneously resolves to  $\leq$ Grade 1 without intervention within 24 hours, the SRC may decide to exempt the laboratory abnormality from being considered a DLT.
- Any treatment-emergent adverse event (TEAE) that leads to study withdrawal of a subject confirmed to have received PB2452.

### **3.4.2.4 Stopping Criteria**

Dose escalation or ongoing infusions will be suspended, pending investigation by the SRC, if any of the following occur after confirmation the subject has received PB2452:

- Any preclinical or clinical events that, in the opinion of the SRC, contraindicate further dosing of additional subjects with PB2452
- Any serious AE (SAE) occurring prior to discharge from the clinical site
- Data from previous cohorts indicate safety concerns for dosing at a higher level, such as unanticipated adverse responses (e.g., CS changes in clinical laboratory test data, ECGs Holter monitoring results, vital signs, physical examinations)
- Two or more subjects in a cohort experience any DLT, or 1 subject experiences a  $\geq$ Grade 2 AE (DLT) that, in the opinion of the SRC, warrants suspension of dose escalation
- Two or more subjects have  $>3 \times$  ULN of either alanine aminotransferase (ALT) or aspartate aminotransferase (AST), or  $>2 \times$  ULN of bilirubin or alkaline phosphatase (ALP) when no other reason can be found to explain the increases
- One or more subjects experiences a  $\geq$ Grade 2 IRR despite having been premedicated for IRRs.

Continuation of dosing following suspension will be determined by the SRC and documented in an ad hoc SRC Safety Report. Dosing may also be suspended if, in the opinion of the SRC or Sponsor, any new or unexpected significant safety or tolerability issues related to ticagrelor or PB2452 are identified that warrant further evaluation before additional subjects are dosed. This may include emerging nonclinical data, clinically relevant AEs, or relevant data from other sources indicating safety concerns, even if the event(s) per se does not meet the protocol-specified definition of a DLT.

Dose-limiting toxicities identified during the study will be assessed as potential indicators of cumulative toxicity and provide rationale for defining the maximum tolerated dose (MTD). Although this study is not designed to dose to a MTD, the MTD may be reached if  $\geq 2$  subjects in a dose cohort experience a DLT, as defined in [Section 3.4.2.3](#). There will be no further dosing above the MTD.

### **3.4.3 Identity of Investigational Product**

Study drug PB2452 is supplied as a sterile white to off-white lyophilized cake, free from visible foreign particles in a 20R glass vial at a nominal fill volume of 7.5 mL. PB2452 in the reconstituted state is formulated at 100 mg/mL in 25 mM histidine/histidine hydrochloride buffer, 290 mM sucrose, and 0.05% (w/v) polysorbate-80, pH 6.0.

Matching placebo is a sterile, nonpyrogenic liquid product intended for IV administration composed of 0.9% sodium chloride in water for injection, USP. Separate instructions will be provided to the clinic for dose dilution, preparation, storage, and administration.

### **3.4.4 Management of Clinical Supplies**

#### **3.4.4.1 Packaging and Storage**

PhaseBio Pharmaceuticals, Inc will provide the investigator and clinical site with adequate quantities of PB2452, and matching placebo. The study site will purchase commercially available ticagrelor 90 mg tablets and ASA 81 mg tablets.

PB2452 will be supplied in a 20R glass vial at a nominal fill volume of 7.5 mL, stoppered with siliconized 20 mm chlorobutyl elastomer, flurotec-coated, single vent lyophilization stopper, and sealed with flip-off cap overseal. Following reconstitution with water for injection, PB2452 is further diluted into 0.9% saline for IV infusion.

The clinical site pharmacy will prepare a single dose for each subject based on the dosing cohort and randomization assignment. The concentration will vary between 0.4 mg/mL up to 72 mg/mL. Separate instructions will be provided to the clinic for dose dilution, preparation, storage, and administration.

PB2452 must be stored in a secure area (e.g., a locked, temperature-controlled unit) at 2°C to 8°C (36°F to 46°F) protected from moisture and light with access restricted to necessary clinic personnel. with access restricted to necessary clinic personnel. The clinical site will be required to keep a temperature log to establish a record of compliance with these storage conditions.

